Lung cancer is the leading cause of cancer death in the US and worldwide. In 2011, approximately 221,130 new cases of lung or bronchial cancer were expected to be diagnosed in the US, and 156,940 patients (71%) are estimated to die of this disease (Siegel *et al.*, 2011). Approximately 64% of non-small-cell lung cancer (NSCLC) patients and 54% of small-cell lung cancer (SCLC) patients will require radiotherapy at least once (Tyldesley *et al.*, 2001). Stereotactic body radiotherapy (SBRT) has provided excellent clinical outcomes for early stage NSCLC, e.g., three-year local control, 98%; three-year survival, 56% in the Radiation Therapy Oncology Group (RTOG) 0236 trial (Timmerman *et al.*, 2010). For advanced stage NSCLC, however, Machtay *et al.* have recently reported a five-year survival rate of 15% for patients treated with chemoradiotherapy from seven RTOG trials (Machtay *et al.*, 2012). The maximum tolerated dose is limited by the risk of toxicity, especially for advanced disease. For example, an attempt to escalate the prescribed dose in the early Phase I portion of RTOG 0117 was unsuccessful because of severe toxicity, including Grade 3 and 5 radiation pneumonitis (Bradley *et al.*, 2005b). Radiation pneumonitis is a common, potentially fatal toxicity that occurs in 5-30% of lung cancer patients treated with radiotherapy (Marks *et al.*, 2010; Palma *et al.*, 2013).

1.2. Personalized radiotherapy that avoids high-functional lung regions may reduce toxicity and facilitate safe investigations designed to improve tumor control

To address the critical problem described above, we propose a novel paradigm, *i.e.*, functional image-guided personalized radiotherapy that avoids high-functional lung regions. It may reduce toxicity and facilitate safe investigations designed to improve tumor control. This hypothesis is supported by several findings in the literature. Abratt *et al.* have found that patients whose irradiated lung regions had >35% of the total lung perfusion are significantly more likely to manifest post-treatment decreases in diffusing capacity and worsening of dyspnea score (Abratt *et al.*, 1990). Seppenwoolde *et al.* (Seppenwoolde *et al.*, 2004) and Vinogradskiy *et al.* (Vinogradskiy *et al.*, 2013) have demonstrated better correlations between the function-weighted lung dose and pneumonitis than those between the physical lung dose and pneumonitis.

1.3. Novel lung ventilation imaging based on 4D CT has high translational potential and advantages

4D CT ventilation imaging is a novel promising technique (Guerrero *et al.*, 2005) (Figure 1) that has high translational potential and advantages (e.g., higher resolution, lower cost, and/or greater availability) over competing modalities. Thus, there has been growing interest in using this technology for functional avoidance treatment planning (Yaremko *et al.*, 2007; Yamamoto *et al.*, 2011) and treatment/toxicity assessment (Ding *et al.*, 2010; Vinogradskiy *et al.*, 2012). Animal studies have demonstrated high accuracy, e.g., correlation with xenon (Xe)-CT ventilation as reference (Fuld *et al.*, 2008; Reinhardt *et al.*, 2008; Ding *et al.*, 2012) as well as high reproducibility (Du *et al.*, 2012). Human studies have reported relatively inconsistent results (Castillo *et al.*, 2010; Castillo *et al.*, 2012; Du *et al.*, 2012; Mathew *et al.*, 2012; Yamamoto *et al.*, 2012; Yamamoto *et al.*, 2014), but reasonable correlations with PFT parameters (Yamamoto *et al.*, 2014), SPECT ventilation (Yamamoto *et al.*, 2014), hyperpolarized ³He MR ventilation (Mathew *et al.*, 2012) and SPECT perfusion (Castillo *et al.*, 2012) indicate the potential for 4D CT ventilation imaging to have physiological significance.

[figure not shown]

Figure 1. Schematic diagram for 4D CT ventilation imaging through (1) acquisition of 4D CT scans, (2) spatial mapping of different respiratory phases of 4D CT images using DIR, deriving a displacement vector field, and (3) analysis of the resultant displacement vector field to quantify regional volume change, a surrogate for ventilation.

1.4. We propose a novel paradigm, 4D CT ventilation image-guided personalized radiotherapy to improve therapeutic gains

Many investigators have demonstrated a dosimetric benefit of functional image-guided radiotherapy that avoids high-functional lung regions using various modalities, including SPECT perfusion (Marks *et al.*, 1995), hyperpolarized gas magnetic resonance (MR) ventilation (Ireland *et al.*, 2007) and 4D CT ventilation (Yaremko *et al.*, 2007; Yamamoto *et al.*, 2011). We have demonstrated that 4D CT ventilation image-guided radiotherapy planning reduces the mean dose to high-functional lung regions by 2 Gy on average compared to anatomic image-guided planning (Yamamoto *et al.*, 2011), indicating that 4D CT ventilation image-guided radiotherapy is estimated to reduce pneumonitis by 4%, corresponding to over 5,000 patients/year in the US, based on the fact that about 60% (Tyldesley *et al.*, 2001) of 221,130 new lung cancer patients (Siegel *et al.*, 2011) are treated with radiotherapy. It is assumed that the probability of pneumonitis increases with the mean dose to high-functional lung regions in a similar manner to the published data on the mean dose to the total lung (Marks *et al.*, 2010). There have been no attempts to assess the safety/feasibility or clinical significance of such treatment in human subjects. In this clinical trial, we will assess the safety and feasibility of 4D CT ventilation image-guided personalized radiotherapy. We will deliver personalized radiotherapy treatments for lung cancer patients, and follow up patients to assess the safety and feasibility. The hypothesis to be tested is: *4D CT ventilation image-guided personalized radiotherapy can be delivered safely for lung cancer.*

2. Specific Objectives and Hypotheses

2.1. Primary objective and hypothesis

Objective: Assess the safety and feasibility of 4D CT ventilation image-guided personalized radiotherapy that selectively avoids irradiating highly-functional lung regions for lung cancer.

Hypothesis: 4D CT ventilation image-guided personalized radiotherapy can be delivered safely for lung cancer.

2.2. Secondary objectives

- 1) Assess long-term toxicity from 4D CT ventilation image-guided personalized radiotherapy as scored by the NCI-Common Terminology Criteria for Adverse Events (CTCAE) version 4.0.
- 2) Estimate the clinical significance of 4D CT ventilation image-guided personalized radiotherapy by evaluating: (1) clinical and subclinical endpoints for pulmonary toxicity (including symptomatic radiation pneumonitis and post-treatment changes in pulmonary function tests (PFTs), 6-min walk test, and BODE index); (2) correlation between those endpoints and functional dose-volume parameters.
- 3) Assess local tumor control after 4D CT ventilation image-guided personalized radiotherapy.
- 4) Quantify the dosimetric significance of 4D CT ventilation image-guided adaptive radiotherapy.

- 5) Investigate whether in vivo EPID dosimetry can detect clinically significant anatomic changes for patients treated with CFRT.

3. Patient Selection

3.1. Inclusion criteria

- 1) Primary lung cancer or metastatic disease to the lungs to be treated with either conventionally-fractionated radiotherapy (CFRT) or hypo-fractionated stereotactic ablative radiotherapy (SABR).
- 2) Age restriction and/or gender/ethnic restrictions: Patients must be ≥ 18 years of age. There are no gender or ethnic restrictions.
- 3) Concurrent chemotherapy is allowed, but not required.
- 4) Life expectancy with treatment should be ≥ 6 months in the estimation of the treating physicians.
- 5) Zubrod performance status ≤ 2
- 6) Adequate marrow and hepatic function defined as Hgb ≥ 8 ; platelets $\geq 100k$; ANC ≥ 1500 ; LFTs $\leq 2x$ upper limit of normal and creatinine ≤ 2.0 or creatinine clearance of ≥ 40
- 7) Patient must be able to provide study specific informed consent prior to study entry.

3.2. Exclusion criteria

- 1) Prior radiotherapy for thoracic cancer or other malignancy leading to any overlap of planned radiotherapy fields.
- 2) For patients undergoing definitive CFRT, patients with distant metastatic disease are not eligible.
- 3) For patients undergoing SABR, both early stage primary lung cancer patients and those with limited metastatic disease to the lungs are eligible; however, patients with oligometastatic disease should have a controlled primary and no more than one other involved organ system.
- 4) Children (< 18 years of age), pregnant women, University of California employees and students, and prisoners will be excluded from this study.
- 5) We will carefully consider the inclusion of patients with severe artifacts in 4D CT images, which deteriorate the accuracy of ventilation computation.

4. Imaging Procedures

4.1. Scans to be acquired

Patients will be positioned in the supine position on a flat tabletop with immobilization (a customized thermoplastic immobilization cast or a molded foam cradle for stabilization for CFRT; a stereotactic body frame or BodyFIX system for SABR). Abdominal compression will be used for all SABR patients unless tumor motion < 1 cm can be reliably demonstrated by fluoroscopy and confirmed by 4D CT without compression. The following scans will be obtained:

Simulation imaging

- 1) Free-breathing CT extending from the angle of the mandible cranially to the inferior extent of the liver caudally at a slice thickness of ≤ 3 mm for CFRT and ≤ 2 mm for SABR. IV contrast to assist in delineation of the mediastinal nodal regions is permitted but not required.
- 2) Pre-treatment 4D CT scan to include lungs from apices to diaphragm and full disease extent.
- 3) If abdominal compression is used, an additional 4D CT scan will be acquired without abdominal compression.

During a course of treatment (CFRT only)

- 1) Two mid-treatment free-breathing CT scans performed at 16-20 Gy and 30-34 Gy to include lungs from apices to diaphragm and full disease extent based on the same method as simulation.
- 2) Two mid-treatment 4D CT scans performed with the mid-treatment free-breathing CT scans to include lungs from apices to diaphragm and full disease extent.

4.2. 4D CT ventilation computation

4D CT ventilation images at the peak-inhale phase will be created using a software tool developed and provided by a collaborator, [name] at Philips Research. This software has not received regulatory clearance. This tool loads anonymized 4D CT images acquired at UC Davis as input, and provides ventilation images calculated based on a non-parametric/volumetric DIR algorithm (Staring *et al.*, 2010) and two classes of ventilation metric: Hounsfield unit (HU)-change (Simon, 2000; Fuld *et al.*, 2008) and Jacobian (Reinhardt *et al.*, 2008) as output.

5. Radiation Therapy

5.1. Dose specifications

CFRT

Patients undergoing CFRT will receive a total of 60 Gy in 30 fractions. The plan will be normalized such that $\geq 95\%$ of the PTV receives the prescription dose. Minimum dose to the PTV (defined as the dose to the lowest 0.03 cc) must be $\geq 90\%$ of the prescription dose ($\geq 85\%$ will be scored as a minor deviation) and maximum dose must be $\leq 115\%$ of the prescription dose to ≤ 0.03 cc ($\leq 120\%$ will be scored as a minor deviation).

SABR

Patients undergoing SABR will receive a total of 54 Gy in 3 fractions for peripheral tumors or 55 Gy in 5 fractions for centrally located tumors (defined as within 2 cm of the proximal bronchial tree or PTV touching mediastinal structures or pleura; tumors with significant chest wall overlap of PTV can also be treated over 5 fractions at treating physician discretion). The prescription isodose surface will be chosen such that 95% of the target volume (PTV) is conformally covered by the prescription isodose surface and 99% of the target volume (PTV) receives a minimum of 90% of the prescription dose.

5.2. Technical parameters

Radiotherapy will be delivered by intensity-modulated radiotherapy (IMRT) or volumetric modulated arc therapy (VMAT) with an Elekta linear accelerator at energies ≥ 6 MV. The dose behind the patient, i.e., transmission dose images will be acquired with a linear accelerator-mounted electronic portal imaging device (EPID). The acquired data will be analyzed with a research version of the PerFRACTION software (Sun Nuclear, Melbourne, FL) (not FDA-approved/cleared).

5.3. Immobilization and simulation

See section 4.

5.4. Treatment planning

Treatment plans will be created using a research version and a clinical version of the Pinnacle treatment planning system (Philips Radiation Oncology Systems, Fitchburg, WI). The research version has not received regulatory clearance, whereas the clinical version has a FDA 510(k) clearance and is routinely used for treatment planning in the Department of Radiation Oncology. First, the research version will be used to create an initial 4D CT ventilation image-guided treatment plan. The initial plan will then be transferred to the clinical version for final dose calculation and evaluation by a radiation oncologist to ensure that the plan quality is clinically appropriate, i.e., target coverage is adequate and critical structures are spared as necessary.

5.4.1. Target volumes

CFRT

- 1) GTV: Will include visible tumor as identified by diagnostic and/or treatment planning CT or PET, including pathologically enlarged lymph nodes >1 cm in short axis, hypermetabolic by PET (SUV >3), or pathologically confirmed to contain malignant cells. Elective treatment of nodal areas is not permitted.
- 2) CTV: A CTV margin of 5-10 mm will be added at the discretion of the treating physician to account for potential microscopic spread. This margin may be shaved off overlapping adjacent structures including chest wall, heart, esophagus, great vessels, and vertebral bodies.
- 3) ITV: Will include the full range of tumor motion of the primary tumor and nodal target as delineated by 4D CT. Depending upon tumor location, a maximum intensity projection or maximal inhale/exhale scans may be used to identify the ITV.
- 4) PTV: An additional margin of 5-10 mm will be added to account for setup error.

SABR

- 1) GTV: Will include visible tumor as identified by diagnostic and/or treatment planning CT or PET.
- 2) CTV: No additional margin for microscopic spread will be used. For purposes of this protocol, ITV=CTV.
- 3) ITV: Will include the full range of tumor motion of the primary tumor and nodal target as delineated by 4D CT. Depending upon tumor location, a maximum intensity projection or maximal inhale/exhale scans may be used to identify the ITV.
- 4) PTV: An additional margin of 5 mm will be added to account for setup error.

5.4.2. Lungs

We will create 4D CT ventilation image-guided personalized radiotherapy plans that selectively avoid irradiating highly-functional lung regions. The peak-inhale 4D CT ventilation image will be aligned with the free-breathing CT image (primary image set for treatment planning) by rigid image registration. The overlapped lungs between the free-breathing CT and peak-inhale 4D CT images will be contoured. Note that the final total lung volume for dose-volume analysis will include combined right and left lungs, excluding the GTV, trachea, and main and lobar bronchi. IMRT or VMAT optimization will be performed by setting higher weights to highly-functional lung regions than poorly-functional regions to meet the dose-volume constraints shown below.

CFRT

Tissue	Constraints
Lung (right and left minus CTV)	$V_{20} < 37\%$ (<40% will be scored as a minor deviation) Mean lung dose (MLD) <20 Gy (<21 Gy will be scored as a minor deviation) Functional $V_{20} < 30\%$ (Vinogradskiy et al. , 2013) (<33% will be scored as a minor deviation) Functional MLD <19 Gy (Vinogradskiy et al. , 2013) (<20 Gy will be scored as a minor deviation)

SABR

Tissue	3 fraction			5 fraction		
	Volume	Vol Max	Max to 0.03 cc	Volume	Vol Max	Max to 0.03 cc
Lung (right and left minus CTV)	<1500 cc	10.5 Gy*	NA	<1500 cc	12.5 Gy*	NA
	<1000 cc	11.4 Gy*		<1000 cc	13.5 Gy*	
	Functional $V_{20} < 4\%$ (Barriger et al. , 2012) (<7% will be scored as a minor deviation) Functional MLD <4 Gy (Barriger et al. , 2012) (<5 Gy will be scored as a minor deviation)					

*Constraints marked by asterisk are guidelines and will not be scored as a protocol deviation if not achieved. For SABR in patients with more than one target, the lung dose-function constraints (functional MLD and V20) are guidelines and will not be scored as a protocol deviation if not achieved. **Other constraints represent absolute limits and treatment delivery that cannot meet these constraints will constitute a major protocol violation.**

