9.3. Analysis plan

Primary endpoints: (1) Grade ≥ 3 radiation pneumonitis, (2) grade ≥ 3 esophagitis, (3) other grade ≥ 3 AEs that occur ≤ 12 months after treatment and drop-out defined as definitely, probably, or possibly related to the protocol treatment.

We will estimate the rates of AEs and tolerability with exact 95% confidence intervals. 4D CT ventilation image-guided personalized radiotherapy will be considered safe if AE rates are lower than the following acceptable rates (determined based on the published toxicity data for locally advanced lung cancer patients): (1) grade ≥ 3 radiation pneumonitis, 13% (Jiang *et al.*, 2012), (2) grade ≥ 3 esophagitis, 21% (Wei *et al.*, 2006), and (3) other grade ≥ 3 AEs and drop-out, 20% (Bradley *et al.*, 2015).

Secondary endpoints

Analyses of secondary endpoints will be primarily descriptive rather than hypothesis testing.

Toxicity will be summarized by frequency and exact 95% confidence intervals, overall and separately by grade and organ system.

The clinical significance of 4D CT ventilation image-guided personalized radiotherapy will be estimated by evaluating: (1) clinical and subclinical endpoints for pulmonary toxicity (including radiation pneumonitis, PFTs, 6-min walk test, and BODE index); (2) correlation between those endpoints and functional dose-volume parameters. Radiation pneumonitis will be assessed at follow-up every 3 months for a minimum of 2 years after treatment using the NCI-CTCAE version 4.0. Post-treatment changes in PFTs (including spirometry, lung volumes and diffusing capacity), 6-min walk test, and the BODE index will be evaluated at the time of 6-month follow-up. Using composite treatment plans, the following lung functional dose-volume parameters will be calculated: functional mean lung dose (fMLD), functional V_{20} (fV_{20}) and functional effective dose (fD_{eff}) (Vinogradskiy *et al.*, 2013), which will be correlated with the endpoints for pulmonary toxicity.

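### The peak-inhale ventilation map is placed on the free-breathing planning CT by rigid registration alone, so functional regions and functional dose figures may be misplaced by an amount the plan does not check.

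*Combined protocol and SAP*

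**What the plan says.** Section 4.2 fixes the geometry of the map: "4D CT ventilation images at the peak-inhale phase will be created". It also says how ventilation is obtained: the tool "provides ventilation images calculated based on a non-parametric/volumetric DIR algorithm". The legend to Figure 1 in section 1.3 describes the same step as "spatial mapping of different respiratory phases of 4D CT images using DIR", after which regional volume change is read from the displacement field.

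Section 5.4.2 then carries the map to the planning scan. The peak-inhale image "will be aligned with the free-breathing CT image (primary image set for treatment planning) by rigid image registration", and the lung common to the two images is contoured. The map sets the optimisation weights. The same section sets limits on functional V20 and functional MLD. Outside the minor-deviation bands, and except for SABR with more than one target, missing them is a major violation.

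Section 4.1 adds a second scan for some SABR patients: "If abdominal compression is used, an additional 4D CT scan will be acquired without abdominal compression". No section says which of the two 4D CTs supplies the map.

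Section 9.3 uses the map again: "Using composite treatment plans, the following lung functional dose-volume parameters will be calculated", namely fMLD, fV20 and fDeff, which are then related to pulmonary toxicity. It also compares functional dose between ventilation-guided adaptive, ventilation-guided non-adaptive and anatomical plans. It does not say how the map is registered for these analyses. No registration tolerance, check or alternative mapping is stated anywhere.

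**The concern.** The method exists because lung tissue moves and changes volume between breathing phases. It measures that change with deformable registration, then places the result on a scan in another breathing state with a transform that allows no volume change. Tissue labelled as highly functional may then sit on its neighbour in the planning CT.

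Three uses are exposed: which lung the optimiser spares, whether a plan meets the functional limits in section 5.4.2, and the functional dose values in section 9.3. The plan comparison in section 9.3 carries a particular risk. If ventilation-guided plans are optimised on a misplaced map and scored on that same map, they are credited for sparing what the map shows. The anatomical plan was not fitted to the map and gets no such credit, so the reported gain may be overstated.

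**Working it through.** **1. The text.** A rigid transform has translations and rotations only, so it preserves volume everywhere. Ventilation here is regional volume change. The transform is therefore exact only where there is no volume change to measure. Restricting to shared lung drops lung outside the overlap and leaves tissue inside it where the rigid match put it.

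**2. Yardsticks in the plan.** There is no stated registration error to reproduce. The relevant margins are:
- fMLD minor-deviation band (5.4.2): 20 − 19 = 1 Gy for CFRT; 5 − 4 = 1 Gy for SABR.
- fV20 band (5.4.2): 33 − 30 = 3 points for CFRT; 7 − 4 = 3 points for SABR.
- Expected gain (1.4): 2 Gy on average. This is mean dose to high-functional regions, so it is close to fMLD but not identical.

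**3. A 1-D model; every setting is assumed.** Lung length L = 24 cm. A 60 Gy plateau of half-width 4 cm is centred 6, 12 or 18 cm from the apex. Displacement u(x) rises from 0 at the apex to U at the base, and ventilation is w = du/dx. The protocol gives no formula for fMLD, so take fMLD = Σ wD / Σ w, with fV20 as the w-weighted percentage at 20 Gy or more. Hand check for uniform w: 60 × 8 / 24 = 20.0 Gy (model 19.8 to 20.1). For w proportional to x with dose at 12 cm: 60 × (16² − 8²) / 24² = 20.0 Gy (model 20.1).

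Error in fMLD (rigid minus correct, Gy) at U = 1 cm, for dose at 6 / 12 / 18 cm:

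| Ventilation pattern | Bone match, no shift | Best mean shift |
|---|---|---|
| Uniform | 0.0 / 0.0 / 0.0 | 0.0 / 0.0 / 0.0 |
| Basal | +0.14 / +0.10 / −0.11 | +0.41 / +0.10 / −0.38 |
| Apical | −0.86 / +0.10 / +0.90 | −0.38 / +0.10 / +0.41 |
| Focal upper | −1.52 / +2.63 / +0.07 | −0.05 / −0.70 / −0.29 |
| Focal lower | −0.42 / −2.41 / +0.45 | −0.29 / −0.70 / −0.05 |

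Over all patterns and matches, the absolute fMLD error is 0.0 to 1.3 Gy at U = 0.5 cm, 0.0 to 2.6 Gy at 1.0 cm and 0.0 to 3.9 Gy at 1.5 cm. The absolute fV20 error is 0 to 2.8, 0 to 5.4 and 0 to 7.7 points. With deformable mapping the error is zero by construction, so the model says nothing about deformable error. The dose is CFRT-like; SABR was not modelled.

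**4. A 3D model; also assumed.** Lung height about 25 cm, patchy ventilation (smoothing 10 to 20 mm) with a mild basal gradient, and displacement rising linearly to the base. With 10 to 20 mm at the base, 8 to 27% of the top third of function is mislabelled with no shift, and 3 to 13% after a mean shift. The protocol uses no top-third rule, so a 60 Gy sphere was added to obtain fMLD:
- Radius 45 mm at three heights, 10 to 20 mm displacement: mean absolute error 0.04 to 0.21 Gy, largest 0.65 Gy, mean signed error within about 0.03 Gy of zero.
- A second run of the model with a 60 Gy sphere: mean error 0.02 to 0.27 Gy, largest 0.99 Gy.
- If deformable registration leaves 3 mm of error, it shows no clear gain over a mean-shift rigid match at 5 to 10 mm displacement.

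**5. Where the residual falls.** In the 1-D model with a bone match, the residual is u(x) itself. For the basal pattern, w is proportional to x and u = U(x/L)². At U = 1 cm the residual at peak ventilation is 1.00 cm, and the correlation of u with w is √(45/48) = 0.97. For the apical pattern, u = U[1 − (1 − x/L)²]; the residual at peak ventilation is 0.00 cm and the correlation is −0.97. For the focal patterns the residual at the peak is 0.44 to 0.56 cm, against a maximum of 1.00 cm at the base.

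**The case against.** The best defence is that the effect may be small. In the 3D model the mean fMLD error is at most 0.27 Gy even though many voxels change label. The 2.6 Gy figure needs a focal ventilation pattern, dose at mid-lung and a bone match; the best mean shift brings the worst 1 cm case down to 0.70 Gy. Deformable registration has its own error and may not do better at small displacements. All of this stands, and it is why the point does not ask for the planning map to be replaced.

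Other defences also hold. The secondary analyses are mainly descriptive. The CFRT anatomical V20 and MLD limits, and the physician's review of the final plan under section 5.4, do not depend on the map. Section 4.2 does not say that the tool accepts the free-breathing CT, so the present software may not be able to do the extra step.

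A reader might also infer more than the documents support:
- **That misplacement is greatest where ventilation is greatest.** Ventilation is the gradient of displacement, whereas misplacement is accumulated displacement. Step 5 shows the two can be strongly related in either direction.
- **That every functional dose figure is wrong, or wrong in one direction.** The error is zero for uniform ventilation, at most 0.41 Gy for a basal pattern at 1 cm, and of either sign.
- **That section 4.1 shows displacements of 1 cm or more.** Its 1 cm is a tumour-motion threshold for omitting compression. It is not an estimate of lung displacement between peak inhale and free breathing.

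The defence does not answer the remaining gap: nothing in the plan would show whether the mismatch in a given patient is negligible or not.

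**Conclusion.** The concern holds as an unchecked source of error in the functional regions and in fMLD, fV20 and fDeff. Its size is undetermined. Under assumed displacements of 5 to 20 mm, the fMLD error runs from about 0 to several tenths of a Gy in the 3D model (worst value 0.99 Gy), and up to 2.6 Gy at 1 cm in the 1-D model. The upper end exceeds the 1 Gy band and the 2 Gy expected gain; the lower end does not matter. These are ranges from assumed geometry and dose, not estimates for this trial.

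The primary safety rates are counts of adverse events and are not computed from the map, so their calculation is unaffected. The possible overstatement of gain in the section 9.3 plan comparison is conditional on plans being optimised and scored on the same misplaced map, which the text leaves open. It would be tempting to conclude that the delivered plans spare the wrong lung; neither the documents nor the models establish that. The missing statement of which 4D CT is used under compression needs no model: it is a gap in the text. Overall this is a cheap improvement to the analysis.

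**What to change.** In section 9.3:
1. In addition to the rigid placement, map the ventilation image to the free-breathing CT by deformable registration, or use a map on the 4D phase or average that best matches that CT.
2. Compute fMLD, fV20 and fDeff under both mappings and report both, including in the toxicity correlations.
3. Rescore the adaptive, non-adaptive and anatomical plans on the deformably mapped image, without re-optimising them.
4. Report the registration check for each patient.

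In sections 4.1 and 5.4.2, state which 4D CT supplies the map when abdominal compression is used.

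Whether the planning map and the scored functional limits should also use the deformable mapping is for the study team to decide once the checks are in.

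The cost is one extra registration and check per CT set. CFRT patients have up to three sets (simulation and two mid-treatment), so the ceiling is 34 × 3 = 102 if every patient were CFRT. No new scans or patients are needed. The type of registration is one the plan already relies on, although a separate program may be needed if the tool cannot take the free-breathing CT. Deformable registration leaves its own residual error, which is the reason for reporting both versions.
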